Participants will be asked to fill out the STAI questionnaire to assess the level of anxiety prior to placement of the labor epidural catheter, and before knowing their group assignment. They will then complete the pre procedure questionnaire. This questionnaire asks about expectations she has for the labor epidural procedure. They will then be given the page of the Newest Vital Signs questionnaire with the Nutrition Facts, and be asked the 6 questions by the recruiter. Then they will be asked the Pain Catastrophizing Scale questionnaire with 13 statements, and asked to respond as directed by the instructions stated by the researcher. They will then be asked who their primary support person is. A form will be handed to that person to confidentially record if he/she would prefer to be present for the procedure. This form will be collected from the support person, and without the parturient aware of the support person's response, she will be asked for her preference with regard to the presence of a support person in

the room, which will be recorded on this form as well. Finally, she will be asked which ethnicity she most relates to, also to be recorded on this form.

After all these data have been collected, the parturient will be randomized as to whether her companion will be allowed in the room or will be asked to leave. This will not be communicated to the parturient until the time of the labor epidural catheter placement. When she requests the neuraxial labor analgesia, the provider placing the labor epidural catheter will be made aware of which group she has been randomized to, and will either ask the companion to leave for placement, or provide the companion a non-mobile chair to sit on in front of the parturient for placement of the labor epidural. The companion will be asked to remain in the chair. He/she will be asked to focus on the parturient. It will be emphasized that he/she must remain seated and will not be allowed to observe the procedure being performed. This is to prevent loss of consciousness in the companion, which has been documented in the literature (Devore and Asrani, 1978; Crosby and Halpern, 1989). One violation will result in a warning, and after a second the companion will be escorted out of the room and the participant will be removed from the study.

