The provider will place the labor epidural catheter in the regular fashion, as is common practice at Prentice Women's Hospital. After preparation and draping of the skin in the sitting position, infiltration with Lidocaine 1% will be conducted at L3-L4 or L4-L5. A 17g Tuohy needle will be advanced into the epidural space, using a loss of resistance with either saline or air, depending on the provider's preference. After the epidural space has been located, a 27g pencil-tip spinal needle will be placed through the Tuohy, into the intrathecal space, and an intrathecal dose of medication will be administered. The exact dose to be injected will be left up to the discretion of the provider, who will determine the appropriate dose based on the patient's situation at that time. After the intrathecal dose is administered, the spinal needle will be removed and a 19g epidural catheter will be placed through the Tuohy into the epidural space. It will be secured at the skin with a sterile dressing and tape, leaving 5cm of the catheter in the epidural space. The patient will then be placed in a lateral position.

After the completion of the neuraxial procedure, the study participant will be asked to record her overall satisfaction with the procedure, as well as her perception of pain during the placement of the labor epidural catheter, using two VAS from 0-100mm. Additionally, she will be asked to complete the STAI questionnaire again. Finally, she will be asked to complete the post procedural questionnaire. At that point the parturient's participation in the study will be complete.

The provider or research team member will be asked to fill out the Participant's Demographics Information form.

The provider placing the labor epidural catheter will be asked to evaluate his/her ability to palpate landmarks for placement, the positioning of the patient, and overall perceived difficulty with the epidural placement, using a VAS from 0-100mm for each, which will be kept confidential. Additionally, they will complete a short series of questions focusing on

the presence of a companion for the procedure. No identifying information from the provider will be recorded on this form.

DATA AND SPECIMEN BANKING:

N/A

DATA AND SPECIMEN MANAGEMENT:

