Group sample sizes of 75 and 75 achieve 81% power to show a difference in means when there is a difference of 4.7 between the null hypothesis mean difference of 0.0 and the actual mean difference of -4.7 at the 0.050 significance level (alpha) using a two-sided Mann-Whitney-Wilcoxon Test.

The acquired data forms will be kept in folders with only the study ID number as an identifier. These folders will be placed in a secure, locked cabinet in the Office of the Section of Obstetrical Anesthesiology. Only those researchers directly analyzing these data will have access to the files. Any electronic communication regarding the study will be conducted using the secure Northwestern email service. Computerized data forms will be password protected. Only the study ID number will be used to identify participants during data analysis. The data will be stored until the completion of the study, including the final data analysis. Members of the anesthesia team collecting these data will be educated on the process prior to approaching prospective participants.

These data collected from each participant will include:

- STAI forms before and after epidural placement
- Pre and post procedure questionnaire
- VAS scoring of satisfaction and pain perception following the procedure
- Newest Vital Sign form completed before epidural placement
- Pain Catastrophizing Score form completed before epidural placement
- Relation of the support person to the parturient
- Support person and parturients preference completed before epidural placement
- Post procedure questionnaire from the Resident/Fellow Physician
- Post procedure questionnaire from the Attending Physician

PROVISIONS TO MONITOR THE DATA TO ENSURE THE SAFETY OF PARTICIPANTS:

N/A

WITHDRAWAL OF PARTICIPANTS:

Participants will be withdrawn from the study if the companion is required to leave due to violation of directions. These include entering the room before the procedure is completed if he/she is in the partner out group, getting up from the chair or attempting to watch the procedure after a warning in the partner in group. When a participant withdraws, data collected up to that point will be retained and analyzed at the end of the study to determine if there is an identifying characteristic that predisposes to inability to follow instructions for safe participation with the epidural procedure.

RISKS TO PARTICIPANTS:

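### Women are removed after randomisation for companion conduct, before their outcomes are collected, and no analysis set is named, so by inference the arms are compared on completers only

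*Combined protocol and SAP*

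**What the plan says.** Under PROCEDURES INVOLVED, the baseline forms come first and then allocation: "After all these data have been collected, the parturient will be randomized". The companion in the room is told to stay seated and not to watch. The sanction is stepwise: "One violation will result in a warning, and after a second the companion will be escorted out of the room". The same sentence also removes the woman: "the companion will be escorted out of the room and the participant will be removed from the study".

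WITHDRAWAL OF PARTICIPANTS repeats the removal ("Participants will be withdrawn from the study if the companion is required to leave due to violation of directions") and lists the triggers for both arms: "entering the room before the procedure is completed if he/she is in the partner out group, getting up from the chair". For the companion-in arm it adds trying to watch, and it applies a warning there.

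The outcomes come later: "After the completion of the neuraxial procedure, the study participant will be asked to record her overall satisfaction with the procedure". The pain VAS, second STAI and post-procedure questionnaire are collected at the same stage.

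For a withdrawn woman, "data collected up to that point will be retained and analyzed at the end of the study". The one stated purpose is "to determine if there is an identifying characteristic that predisposes to inability to follow instructions".

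NUMBER OF LOCAL PARTICIPANTS sets the target as 150 women who complete, 75 per arm. It plans to recruit 180 to cover losses by choice or protocol violation, and expects few women to become ineligible. No section names an analysis set or a rule for missing outcomes.

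**The concern.** Randomisation protects the comparison only while women are analysed as they were allocated. Here a woman can be lost because of something that happens after allocation, and the event depends on the arm. In companion-in, removal follows the companion being sent out. In companion-out, it follows the companion coming in. In the survey reported under BACKGROUND, 29 of 34 women (85%) said they would want a companion, so the two events need not bear on satisfaction alike. That does not tell us which way a bias would run.

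The loss is also permanent. The retained data would show who was removed, but not how satisfied they were. Neither an as-assigned analysis nor a check on the size of any bias could be rebuilt afterwards. Recruiting extra women restores the numbers but does not correct selection.

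**Working it through.** **1. Order of events.** Baseline forms, then randomisation, then the procedure (when the triggers occur), then satisfaction, pain and second STAI. Every trigger falls before the outcomes. That the comparison is of completers is an inference from this order, the completer target, the counting of violations as drop-outs and the absence of a named analysis set. It is not stated text.

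**2. The plan's own figure.** DATA AND SPECIMEN MANAGEMENT gives 81% power for a difference of 4.7 with 75 per group, two-sided 5%, Mann-Whitney-Wilcoxon, but no SD. I used power = Φ(4.7/SE − 1.96), with SE = SD × √(2/n).
- With n = 75, 81% implies SD 10.1.
- With n = 75 × 3/π = 71.6 (Mann-Whitney efficiency for normal data), it implies SD 9.9.
- At SD 10 the two versions give 82% and 80%.

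SD 10 is therefore a fair working value. It remains an assumption, because the power statement names neither the outcome nor the scale of the 4.7.

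**3. Bias formula.** In one arm let *p* be the share removed, *K* the mean satisfaction of the women kept, and *g* how much lower the removed women would have scored. The as-assigned mean is (1 − p)K + p(K − g) = K − pg, so the completer mean is too high by pg. For in minus out:

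bias = p_in × g_in − p_out × g_out

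Equal removal gives zero only if the deficits are equal too: 10% from each arm with deficits of 10 and 10 gives 0, but with 10 and 0 it gives 1.0 mm. Unequal removal can also cancel: 10% × 10 − 5% × 20 = 0.

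**4. Illustration (all inputs assumed).** 75 analysed per arm, SD 10, no true difference, one arm affected, g = 10 mm. SE = 10 × √(2/71.6) = 1.67. Type I error = Φ(−1.96 + b/SE) + Φ(−1.96 − b/SE), where b is the bias.

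| Removed in one arm | Bias b | Type I error, formula | Type I error, simulated Mann-Whitney |
|---|---|---|---|
| 3% | 0.03 × 10 = 0.3 mm | 5.4% | about 5% |
| 10% | 0.10 × 10 = 1.0 mm | 9.2% | about 9% |

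If 180 are randomised evenly (90 per arm), these shares are about 3 and 9 women. With a wider spread the effect shrinks: the 10% case gives about 7% at SD 15 and 6% at SD 20.

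**5. Cost of keeping everyone (dilution).** Suppose a true 4.7 difference (SD 10) is wholly lost in the non-adherent women of one arm. The expected difference is 4.7 × (1 − share).

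| Non-adherent in one arm | Expected difference | Simulated power |
|---|---|---|
| none | 4.7 | 79% (80% by formula) |
| 3% | 4.56 | 77% (75 v 75) to 78% (77 v 75) |
| 10% | 4.23 | 70% (75 v 75) to 73% (83 v 75) |

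The upper ends keep 75 adherent women in the affected arm and add the non-adherent ones to it (75/0.97 ≈ 77; 75/0.90 ≈ 83).

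**The case against.** **Violations may be very rare.** Few women are expected to become ineligible, the seated companion gets a warning first, and the chair does not move. This stands. At 3% removal the illustrated effect is negligible.

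**Different triggers are not in themselves a defect.** One companion is inside the room and the other outside, so their possible violations must differ. This also stands. The weakness is the stopped follow-up and the unnamed analysis set; the different triggers only mean that balance cannot be assumed.

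**The plan retains data, and lists VAS and STAI forms among the data from each participant.** Retention covers only what exists at withdrawal, and a general list does not override an explicit removal. If these outcomes are meant to be collected after a violation, the text should say so.

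**Keeping non-adherent women dilutes the effect of a companion actually being present, which is what STUDY ENDPOINTS asks about.** This is a fair trade-off, and the violation-free sensitivity analysis serves that question.

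A reader might also infer that the sections contradict one another on when a warning is given. They do not. The warning under PROCEDURES INVOLVED concerns the seated companion and agrees with WITHDRAWAL OF PARTICIPANTS. The consent section naturally speaks only of companion-in, since the other companion has already been asked to leave. What remains is an omission: the plan does not say whether a warning applies in companion-out.

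**Conclusion.** The point holds as a cheap improvement. The text establishes removal after randomisation, before the woman's own outcomes, with no analysis set named. The completer comparison is a reasonable inference. The sign and size of any bias are unknown and materiality is not shown. The 0.3 mm and 1.0 mm figures rest wholly on assumed removal rates, an assumed deficit and an assumed SD.

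Three stronger readings are not supported:
- **Serious error inflation.** A type I error of about 22% needs a bias of 2.0 mm, for example 10% removed from both arms with removed women 10 mm less satisfied in one arm and 10 mm more satisfied in the other. Nothing in the documents supports those inputs.
- **Using the 20% drop-out allowance as a violation rate.** It covers all causes and is not a difference between arms.
- **Loss of every post-procedure measure.** The woman's own VAS and STAI are lost on the written rules, but nothing says the provider's difficulty ratings stop.

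**What to change.** In PROCEDURES INVOLVED and WITHDRAWAL OF PARTICIPANTS, drop the removal of the woman from the study after a companion violation and leave the rule on companions unchanged. Add that:
- her satisfaction VAS, pain VAS, second STAI and post-procedure questionnaire are still collected if she is willing;
- the primary comparison is by assigned group;
- violations are reported by arm and reason;
- the violation-free set is a sensitivity analysis.

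The sponsor should also clarify whether a warning applies in the companion-out arm.

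The cost is a few sentences of protocol text, the same short forms for the few women now removed, and the dilution shown above: on those assumptions, power of about 77–78% at 3% non-adherence and about 70–73% at 10%, against about 80% with none. The change must be made before enrolment, because outcomes not collected at the bedside cannot be recovered.

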Parturients will be included if they are delivering the first child and are planning to labor with neuraxial analgesia. Additionally, there will need to be sufficient time before delivery to allow the completion of the Pre procedure questionnaire, State-Trait Anxiety

Inventory (STAI) questionnaire both before and after the procedure, as well as the Newest Vital Sign questionnaire and the Pain Catastrophizing Scale questionnaire before the procedure. They will be included if they are ASA 2. Furthermore, they be required to read and comprehend the English language, as the Newest Vital Sign questionnaire requires them to read and interpret a nutrition label.

Physician Inclusion:

Anesthesiology Attending, Fellow or Resident Physicians who participants in the placement of the epidural catheter placement

Companion Inclusion:

Primary companion identified by parturient over the age of 18

Exclusion: Parturients will be excluded if they are receiving neuraxial anesthesia for a cesarean delivery, external cephalic version, or other non-labor procedure. They will also be excluded if they begin to push for delivery before completion of the STAI questionnaire following labor epidural catheter placement. They will be excluded if there is no support person present at the time of the neuraxial procedure. They will be excluded if they are ASA 3 or greater, or if they have a contraindication to receiving any of the medications routinely used in the placement of a labor epidural catheter (lidocaine, bupivacaine, epinephrine, fentanyl). Adults who are unable to consent and minors will be excluded.

STUDY-WIDE NUMBER OF PARTICIPANTS:

The total number of participants has been determined to be 75 per group, for a total of 150.

STUDY-WIDE RECRUITMENT METHODS:

Potential participants will be recruited while they are on the labor and delivery ward at Prentice Women's hospital, prior to the placement of a labor epidural catheter. They will be approached by a member of the research team.

Potential participants will be identified by interview and personal history, as well as by anesthesia and obstetric notes in the electronic medical record.

No advertisements will be used to recruit participants for the study.

MULTI-SITE RESEARCH:

N/A

STUDY TIMELINES:

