The duration of an individual's participation extends from initial enrollment while on the labor and delivery ward prior to labor epidural catheter placement until the completion of the STAI questionnaire and survey following this procedure. The duration of the study enrollment is anticipated to be 3-5 months, with the plan to enroll an average of 2-4

parturients daily, and accounting for study drop-outs. The estimated date for study completion is late spring to early summer of 2017.

STUDY ENDPOINTS:

The primary endpoint for the study is:

- Does having a support person present when it is the desire of the parturient has a positive effect on maternal satisfaction during the placement of epidural catheter for labor analgesia?

The secondary endpoints are:

- Does having a support person present when it is the desire of the parturient has a positive effect on maternal anxiety during the placement of epidural catheter for labor analgesia?
- Does having a support person present when it is the desire of the parturient have a positive effect on maternal perception of pain during the placement of epidural catheter for labor analgesia?
- Does the presence of a support person affect the perceived difficulty of the procedure by the provider placing the labor epidural catheter?
- Does the level of health literacy of a parturient affect her level of anxiety?
- Does the degree of Pain Catastrophizing affect the parturients level of anxiety?
- Does the relationship of the parturient to the support person have an effect on the level of anxiety of the parturient?
- Does the ethnicity of the parturient have an effect on the level of anxiety?
- Does induction of labor versus spontaneous labor have an effect on the level of anxiety of the parturient?

PROCEDURES INVOLVED:

Parturients who have been admitted to the Labor and Delivery ward at Prentice Women's Hospital will be approached by a member of the research team prior to the placement of a labor epidural catheter. They will be asked if they are considering neuraxial labor analgesia, and if they are they will be screened using the inclusion and exclusion criteria to determine study eligibility. Once they have been evaluated and found to be appropriate for the study, they will be invited to participate.

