- The member of the anesthesia team recruiting the participants will be educated in the use of the STAI, pre and post procedure, Newest Vital Sign, and Pain Catastrophizing questionnaires prior to enrolling participants. The primary recruitment will be by the anesthesia research nursing staff that has extensive experience in recruiting participants to various studies.
- We expect to recruit 2-4 participants on a daily basis, as the number of labor epidural catheters placed during a given 24 hour period well exceeds 20. By recruiting 1 participant every day (<5% of laboring parturients each day), or 7 in a week period, the data collection would take 22 weeks, which is within the proposed 3-5 month recruitment period.
- This research will be conducted primarily by [name]. and [name]. the latter of which is the current Fellow in Obstetrical Anesthesiology and has 3 months of devoted time during this fellowship year for research.
- While the collection of data will occur in the Labor Suite on the Labor and delivery ward, the analysis of these data collected during the study will be analyzed in the Office of Obstetrical Anesthesiology 9th floor Prentice as well as in the main Anesthesiology Office in Arkes 10th floor. These locations are restricted to personnel in the Department of Anesthesiology and are not located in patient care areas.
- Participants will have access to the members of both the research and anesthesia teams on call, before and after placement of the labor epidural catheter, who can answer any questions they may have regarding the procedure.
- Prior to recruiting participants, the study protocol will be reviewed by the anesthesia research study team.
- The provider placing the labor epidural catheter will be informed of which group the parturient was randomized into just before entering the room for the procedure. At that time they will either ask the companion to leave the room or ensure that there is a non-mobile seat for the companion in front of the parturient.

PRIOR APPROVALS:

Department of Anesthesiology Research Committee

RECRUITMENT METHODS:

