Participants will be recruited on the Labor and Delivery Ward 8th floor of Prentice Women's Hospital. They will be approached regarding participation if they meet inclusion criteria during chart review or initial pre-anesthesia interview. Both patients in spontaneous labor and those scheduled for induction of labor will be approached if they meet criteria. The GE Centricity computerized board that lists all active laboring parturients is available in the anesthesia work room for review of the current Labor and Delivery census. If the patient is nulliparous she will be approached by a member of the

research team with regard to enrollment in the study. No reimbursement will be offered for participation.

NUMBER OF LOCAL PARTICIPANTS:

A total of 150 participants will complete the study. Half of the participants (n=75) will be randomized to the “companion in the room” group and half (n=75) will be randomized to the “companion out of the room” group. We are anticipating minimal patients who enroll to become ineligible during the study, since the total duration of enrollment is likely less than a couple hours, however we will attempt to recruit 180 participants in total to allow for a 20% drop-out rate, either by choice or by protocol violation.

Resident Participation: A total of 64 participants

Attending Physician: A total of 30 participants

Companion: A total of 150 participants

CONFIDENTIALITY:

Data will be stored in a department server which is password protected. Each study subject will be assigned a study code number. The code will be used to link study data to patient identification (name) in a separate database. Subject data will be stored on secured password protected computers at Northwestern University and Department of Anesthesiology servers. Paper data will be completed by research study team members and will be entered into REDCap. The paper folders will be stored in Arkes Pavilion 10th floor Department of Anesthesiology administrative office via key card controlled front door and key controlled closet. Data access will be password protected and only available to study investigators via REDCap. REDCap access will be controlled by the Principal Investigator. Data both electronic and paper will be destroyed 5 years after manuscript preparation.

PROVISIONS TO PROTECT THE PRIVACY INTERESTS OF PARTICIPANTS:

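### Recruiting 180 covers a drop-out of at most 16.7%, not the stated 20%; a full 20% loss would leave 144 completers, not 150.

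*Combined protocol and SAP*

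**What the plan says.** The protocol's Number of Local Participants section fixes the target: "A total of 150 participants will complete the study", split 75 and 75. It then gives the margin for loss: "we will attempt to recruit 180 participants in total to allow for a 20% drop-out rate". In the same sentence it expects the loss to be small: "We are anticipating minimal patients who enroll to become ineligible during the study".

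The 75 per group appears in two other places. Study-Wide Number of Participants states: "The total number of participants has been determined to be 75 per group, for a total of 150". The power statement, placed under Data and Specimen Management, says: "Group sample sizes of 75 and 75 achieve 81% power", for a mean difference of 4.7 with a two-sided Mann-Whitney-Wilcoxon test at 0.05. So 150 is the number that the power calculation requires at analysis, and 180 is meant to protect it.

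Two sections deal with timing. Study Timelines says: "The duration of the study enrollment is anticipated to be 3-5 months, with the plan to enroll an average of 2-4" parturients a day, and adds that drop-outs are taken into account. Resources Available repeats the rate of 2-4 a day and adds an illustration at one a day, concluding that "the data collection would take 22 weeks, which is within the proposed 3-5 month recruitment period".

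**The concern.** A drop-out rate is ordinarily a share of those enrolled. The section reads that way: it speaks of enrolled patients who become ineligible, leave by choice or are lost through a protocol violation. No section defines the rate as a share of completers. On the ordinary meaning, 180 recruits do not yield 150 completers after a 20% loss, so the protocol claims more protection for its sample size than it has.

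What is at stake is the power margin. The stated 81% at 75 per group is one percentage point above 80%, so a modest shortfall can take power below that level. The protocol also names real routes of loss after enrolment: pushing before the second STAI is finished and having no support person at the procedure (Exclusion criteria), and removal for companion violations (Procedures Involved; Withdrawal of Participants). The allowance therefore has work to do, and its size should be stated correctly.

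**Working it through.** **Inputs.** From Number of Local Participants: 150 completers, 180 recruited, 20% drop-out. From Data and Specimen Management: 75 per group, 81% power, two-sided alpha 0.05. The protocol gives no SD; the power step below does not need one.

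**1. Reproduce 180.**
- Completers × (1 + rate): 150 × 1.20 = 180. This matches exactly.
- Completers / (1 − rate): 150 / 0.80 = 187.5, rounded up to 188 (94 per group). This does not match; 180 is 8 too few.

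**2. Loss that 180 covers.** (180 − 150) / 180 = 30/180 = 16.7%.

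**3. Completers from 180 recruits.**

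| Loss | Completers | Against 150 |
|---|---|---|
| 10% | 180 × 0.90 = 162 | +12 |
| 15% | 180 × 0.85 = 153 | +3 |
| 16.7% | 150 | 0 |
| 20% | 180 × 0.80 = 144 | −6 |

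**4. Power at 144 completers.** Assume that the stated 81% is right and that loss is equal, giving 72 per group. In the normal approximation, 81% power at two-sided 0.05 corresponds to a signal of 1.960 + 0.878 = 2.838 at 75 per group. The signal scales with the square root of the group size, so the SD and the efficiency of the Wilcoxon test cancel:
- Signal at 72 per group: 2.838 × √(72/75) = 2.838 × 0.980 = 2.781.
- Power: Φ(2.781 − 1.960) = Φ(0.821) = 79.4%.
- If the stated 81% is itself rounded, a true value of 80.5% gives 78.9% and 81.5% gives 79.9%.
- If loss is unequal, for example 66 and 78, power is about 79.1%.

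**5. Timeline (minor).** The one-a-day illustration matches 150 participants: 150/7 = 21.4 weeks, rounded up to 22. For 180 it is 180/7 = 25.7 weeks, against about 21.7 weeks in five months. At the planned 2-4 a day, 180 takes 180/4 = 45 to 180/2 = 90 days, so the planned rate fits the window comfortably.

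**The case against.** The strongest reply is that this is loose wording with almost no consequence. The 180 is something the team will attempt, the firm target is 150 completers, and the 20% may simply mean a recruitment margin over that target. Participation is expected to last no more than a couple of hours, little loss is foreseen, and nothing in the protocol suggests a rate near 20%. On the same power calculation, an 18% loss still gives 80.4% and a 19% loss gives 79.9%, so power drops below 80% only near the top of the stated allowance.

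Most of this stands as a limit on size. It does not make the sentence correct: the margin is called a drop-out rate, and at that rate 150 do not complete. If a margin of 30 extra recruits was intended, the protocol should say so.

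Two narrower objections are also fair. The figure of 72 per group assumes equal loss, which is not assured because the violation rules differ between the groups; the figure that follows directly from the protocol is 144 in total, and unequal loss changes the power little. The timeline illustration is a cautious aside that may count completers only, and Study Timelines already says that drop-outs are considered. It threatens nothing, and correcting it is optional.

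**Conclusion.** The point holds. As written, the protocol claims an allowance of 20% but provides 16.7%. At the full 20% the trial would be 6 completers short, and power would be about 79.4% instead of 81%, a loss of 1.6 points. The completer figures follow from the protocol's own numbers, with drop-out taken as a share of those recruited. The power figure also assumes that the stated 81% is correct and that loss is equal in the two groups.

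At any loss up to 16.7% there is no shortfall, so this does not show that the trial is underpowered as planned. It is an incorrect statement about sample-size protection that should be corrected; design and analysis are unaffected.

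**What to change.** In Number of Local Participants, do one of the following:

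- Restate the allowance as a drop-out of up to 16.7% (30 of 180). This is the simplest correction.
- Keep 180 and state that a 20% drop-out would leave 144 completers (72 per group if loss is equal) with about 79% power.
- Raise recruitment to 188, only if a full 20% must be covered. At 2-4 a day this takes 188/4 = 47 to 188/2 = 94 days, still within the planned window.

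Optionally, in Resources Available, base the one-a-day illustration on 180 (about 26 weeks) or rely on the planned 2-4 a day.

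The first two options cost one reworded clause and no extra participants. The third costs 8 more recruits.
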